5.2 Handling of Study Interventions

Treatment credibility. It is essential that subjects perceive both interventions as equally credible for promoting a similar degree of expectation for improvement. We will evaluate treatment

credibility, expectation for change, and satisfaction after the 2nd session of treatment and at post-intervention, according to procedures using a 10-point Likert scale, as we have done in our pilot.

5.3 Concomitant Interventions

Alternate treatments. All subjects will be medically stable prior to entry into the study protocol and will be stable on psychotropic medications or ongoing psychotherapy for at least 4 months. However, if subjects engage in alternate treatments (other types of mind-body (e.g. yoga), integrative (e.g., acupuncture), psychotherapy, switching to different antidepressant treatment, or have an elective surgery or hospitalization), they will be advised to inform the PI or a designated staff at every visit. All assessments will be done blindly. If the alternate treatment is judged to affect outcomes of the study, the subject will be withdrawn from the interventions but followed naturally for 6 months. This decision will be made by the PI on the basis of blinded assessments. Subjects will be informed about an option of pursuing clinical care in the community.

The concomitant medication document and any changes will be recorded at each visit. The database will have a variable identifying the type of antidepressants or any other psychotropic drugs or other prescription or over-the –counter medications/supplements that participants are taking. Classes of drugs will be recorded as well.

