1. STUDY OBJECTIVES

1.1 Primary Objective

Aim 1: Evaluate the effects of **TCC** versus **HEW** on reduction of depressive symptoms and improvement in the secondary outcomes during the 12-week treatment trial, in addition to 6 and 12 month follow-up (or 24 months if 12 months have passed).

Hypothesis 1: Compared to **HEW**, **TCC** will result in a) greater reduction of depressive symptoms and b) improvement in the cognitive domains of executive function and memory at 12 weeks, 6 months, and 12-month follow-up (or 24 months if 12 months have passed).

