5. STUDY INTERVENTIONS

5.1 Interventions, Administration, and Duration

Each class will be held for 60 minute per day/week. Homework assignments will be equal in all groups and ask for at least 20 minutes of either TCC, or computer searches on the topics of wellness at home. Participants will be asked to keep diaries of daily exercises, time spent and adherence to the tasks will be compared between the groups, and used as a predictor/mediator in the primary analyses of response. All classes will be offered once a month as booster session for the remainder of the study between weeks 12 and 24. Subjects will be given a DVD of the training course and encouraged to continue practice at home. Subjects in the HEW group will be asked not to join any of the TCC classes until the end of the study. At the end of the study, participants will be offered an option of participating in the two alternative classes.

Tai Chi Chih (TCC): TCC employs “meditation through movement” as a means of helping older adults cope with fatigue, perceived physical limitations, and negative emotional states, which are commonly associated with insomnia. Patients will be informed that TCC constitutes a health management intervention, which incorporates meditation and physical activity to promote a sense of well-being and control over negative symptoms associated with depression. The standard detailed protocol for TCC uses an adapted protocol from the “Tai-Chi-Chih Joy through movement” by Justine F. Stone¹⁴¹ and has been used in several studies by our research group, and others (i.e., R21-AT002307). TCC sessions will be held for 60 min a day once a week. Each class will allow 10 minutes of warm-up (e.g., stretching, breathing), 5 minutes of cool down. Participants will be instructed to practice at home for 20 minutes per day using handouts and documenting their practice in their daily diaries.

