8. INTERVENTION DISCONTINUATION

Subjects have the right to refuse to participate or to withdraw from the research study and discontinue participation at any time. Subjects will continue to be followed with their permission if study intervention is discontinued.

All subjects will be medically stable prior to entry into the study protocol and will be stable on psychotropic medications or ongoing psychotherapy for at least 4 months. However, if subjects engage in alternate treatments, they will be advised to inform the PI at every visit. If the alternate treatment is judged to interfere significantly with the intervention, the subject will be withdrawn from the interventions but followed naturally for 12 months. Subjects will be informed about an option of pursuing clinical care in the community.

Subjects who do not improve or get worse during acute intervention phase or relapse during the continuation phase will be offered treatment outside the protocol in the Geriatric Psychiatry Clinics, or other community clinics. They will also be invited to come for the 6 and 12 month follow-up to determine their progress and the patterns of response to treatment while controlling for any changes in treatment.

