Aim 1: Primary analysis: Our primary analysis will consist of a GLMM for HAMD-24 with treatment group effects and time main effects, along with two-way interactions of time and group. The primary analysis will assess treatment effects at the end of treatment at 12 weeks. Our primary analysis is valid under the assumption of missing-at-random. To study missingness patterns, we will compare mean response trajectories of the primary outcome measure HAMD for subjects who dropped out and those who did not. We will further compare treatment groups for drop-out rates, time to drop-out and drop-out reasons. Since it is theoretically impossible to rule out data missing-not-at-random, we will also perform sensitivity analysis taking a pattern mixture approach. Our pattern mixture approach will make assumptions on how the outcome trajectory

for subjects who dropped out will differ from those for subjects who did not. These differences will be allowed to be vary across treatment arms and the amount of difference will be varied in a plausible range to obtain a full sensitivity analysis.

Secondary analysis: Treatment maintenance will be assessed via the GLMM at follow-up as part of the secondary analysis. Secondary analysis will also include comparison of remission status (binary outcome) at the end of treatment between treatment groups via a logistic regression. Analyses for secondary outcomes clinical global improvement (CGI) and cognitive domain scores in the executive function and memory domains will be similar to those above for the continuous HAMD scores. As noted in the Neuropsychological Assessment section, there are 4 cognitive domains that are being assessed. Of these, the two primary cognitive domains of interest for this proposal are executive function and memory. A separate GLMM as above will be estimated using these 2 domain scores as dependent variables. In addition treatment adherence and time in practice will be considered as moderators of treatment effects in the longitudinal modeling of primary depression and imaging outcomes in the first two aims.

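### Sections 5.3 and 8 give different follow-up lengths (6 and 12 months) after withdrawal for alternate treatment, and the shorter one ends before month 12

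*Combined protocol and SAP*

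**What the plan says.** Two sections deal with a subject who takes up another treatment during the trial.

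- **Section 5.3** (Concomitant Interventions): "If the alternate treatment is judged to affect outcomes of the study", then "the subject will be withdrawn from the interventions but followed naturally for 6 months".
- **Section 8** (Intervention Discontinuation): "If the alternate treatment is judged to interfere significantly with the intervention", then "the subject will be withdrawn from the interventions but followed naturally for 12 months".

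Section 9.4 lists the same event among the stopping rules and gives no follow-up length.

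Month 12 is a named time point. Section 1.1 hypothesizes a greater reduction in depressive symptoms and "improvement in the cognitive domains of executive function and memory at 12 weeks, 6 months, and 12-month follow-up". Section 9.5.2 determines relapse at 6 and 12 months. In section 9.6 the primary time point is earlier: "The primary analysis will assess treatment effects at the end of treatment at 12 weeks". The later comparison is secondary: "Treatment maintenance will be assessed via the GLMM at follow-up as part of the secondary analysis".

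Other sections also bear on follow-up after withdrawal:

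- Section 2.2 includes all participants in the post-intervention follow-ups, also those who worsen and discontinue.
- Section 5.4 follows those who leave the arms for any reason, with no time limit.
- Section 8, in its next paragraph, invites subjects who fail to improve, worsen or relapse to months 6 and 12.
- Section 6 restricts the Month 12/24 visit to participants in the MRI part, planned at 55 per arm.

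**The concern.** The same event and the same action carry two follow-up lengths. Staff handling an alternate treatment would naturally consult section 5.3, the section on that topic, and could stop outcome collection before month 12. Staff following section 8 would not.

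The loss need not be random. Section 2.2 encourages non-responders in follow-up to seek other treatment, and section 5.3 counts a change of antidepressant and psychotherapy as alternate treatments. Poor response can therefore lead to alternate treatment and, under section 5.3, to no month-12 data. If response differs by arm, the loss could differ by arm as well. What is at stake is the secondary month-12 comparison of maintenance and relapse, where the missing-at-random assumption would be under more strain than it need be.

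**Working it through.** **1. The plan's own follow-up figure.** Section 9.2 gives a detectable difference of 0.36 SD at 6 and 12 months with 88 per arm (110 × 0.80 = 88), 80% power, α = 0.05 (two-sided assumed) and correlation ρ = 0.5. For a group-by-linear-time contrast with equal correlations and time scaled 0 to 1,

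d = (1.960 + 0.842) × √[(2/n)(1 − ρ)/Sxx],

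where Sxx is the sum of squared deviations of the visit times.

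- Week 12: n = 99, seven visits, Sxx = 0.778, so d = 0.319 (stated 0.32).
- Follow-up: n = 88, the seven treatment visits plus month 6, Sxx = 0.683, so d = 0.361 (stated 0.36).

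The plan does not say which visits the second figure uses. At d = 0.36, visits at 0, 3, 6 and 12 months give 70.5% power, and all visits to month 12 give 86.4%. The figure is reproducible under a plausible visit set.

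**2. Does section 5.3 reach month 12?** The section does not say when the six months start.

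- From randomization: follow-up ends at month 6.
- From withdrawal at week 0, 12 or 24: it ends at week 26, 38 or 50 (months 6.0, 8.8 and 11.5).

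Week 24 is the last intervention contact: "All classes will be offered once a month as booster session for the remainder of the study between weeks 12 and 24". Month 12 is week 52, or week 51 at the earliest with the one-week window in section 6.2.4. Since 50 < 51, every case ends too early. Twelve months under section 8 reaches month 12 from either start, counting from the same origin as the visits.

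**3. Number lost at month 12.** The documents give no rate of withdrawal for alternate treatment. Assume 10-20%. The base is the 55 per arm in the MRI part (sections 6 and 6.2.1):

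- 0.10 × 55 = 5.5 and 0.20 × 55 = 11, so about 6-11 per arm.

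The planned 20% dropout applied to the same base is 0.20 × 55 = 11 per arm. The documents do not say whether these withdrawals are already counted in it.

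**4. Possible shift in the month-12 contrast.** Assume withdrawn subjects score 0.5 SD worse at month 12 and withdrawal differs by 10 percentage points between arms. If all of them are missing, a complete-data contrast shifts by

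- 0.10 × 0.5 = 0.05 SD.

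The planned mixed model uses earlier visits. With ρ = 0.5 at all lags and ten earlier visits (baseline, six treatment visits, months 4, 5 and 6), each visit has weight 0.5/(1 + 9 × 0.5) = 0.0909 in predicting month 12.

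- Deficit present at all ten visits: 10 × 0.0909 = 91% recovered, leaving 0.05 × 0.09 ≈ 0.005 SD.
- Deficit present only at months 4-6: 3 × 0.0909 = 27% recovered, leaving 0.05 × 0.73 ≈ 0.036 SD.

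**The case against.** The strongest reply is that the plan's intention is clear elsewhere. Section 2.2, section 5.4 and the next paragraph of section 8 all point to continued follow-up of people who stop the intervention, with treatment changes documented and controlled for. Section 6 says the Month 12/24 visit was added to the original study, so the six months in section 5.3 may be leftover wording (an inference). The primary analysis is at week 12, the mixed model uses all observed visits, and section 9.6 plans a pattern-mixture sensitivity analysis with departures that may differ by arm.

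Most of this stands and limits the size of the problem. It does not remove the contradiction: no sentence says section 8 governs, and the other sections only make section 5.3 the outlier. The pattern-mixture analysis is described for HAMD and does not replace data that could be collected.

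Some stronger readings are tempting but not supported:

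- **A loss of 11-22 per arm**, taking 10-20% of 110. Section 6 limits the Month 12/24 visit to MRI participants, so the base is 55.
- **A bias of 0.05 SD, or 14% of the detectable 0.36 SD.** The 0.05 is an upper value from unsourced assumptions for an analysis that is not the planned one, and 0.36 assumes 88 per arm, which the MRI restriction cannot supply at month 12.
- **Loss of poor responders specifically.** Section 5.3 also lists yoga, elective surgery and hospitalization, and withdraws only subjects whose alternate treatment is judged to affect outcomes. A relation to response is plausible but not established.

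**Conclusion.** The plan is wrong as written: sections 5.3 and 8 contradict each other on follow-up after withdrawal for alternate treatment, and section 5.3 also conflicts with sections 2.2 and 5.4. The slight difference in trigger wording does not resolve this, because nothing indicates that the two sections describe different groups. Applied literally, section 5.3 ends follow-up before month 12 in every case.

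The consequence is confined to the secondary month-12 comparison, and its actual size cannot be computed from the documents. The illustration of 6-11 per arm rests on an assumed withdrawal rate and may overlap the planned dropout. The shift of at most about 0.05 SD rests further on the assumed deficit and arm imbalance. The range of roughly 0.005-0.036 SD under the mixed model rests on those and on a constant correlation of 0.5. A reader might infer a threat to the trial's main result, but the week-12 primary analysis does not depend on this follow-up period. Severity is low; correction is worthwhile because it is nearly free.

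**What to change.** Reconcile sections 5.3 and 8 with sections 2.2, 5.4 and 6. State one outcome-assessment period after withdrawal from the interventions, and say that withdrawn subjects have the same follow-up assessments as other subjects, through the last between-arm visit that applies to them. Defining the period by visit rather than by a count of months also settles when the clock starts and covers visits deferred to Month 24.

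Changing one word in section 5.3 would not be enough. Section 6 would still exclude withdrawn subjects outside the MRI part from the Month 12/24 visit, so the text should say which visit is the last for each group.

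The change concerns data collection only and alters no treatment or withdrawal rule. The cost is a short text amendment and a small number of visits that are already planned.

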5.4 Adherence Assessment

SOP: Weekly supervision by PI- [name] with designated study staff will be used to monitor adherence to the intervention and protocol during each group and clinical visit and during weekly staff meetings. Participants will be asked to keep diaries of exercise or computer searches and the adherence will be compared between the groups. Subjects will not be removed from the study due to poor adherence to retain sufficient sample for the analyses. If they decide to drop out from the intervention arms for any reasons, they will be followed naturally. Subjects who miss three or more intervention sessions will be identified as deviation from the protocol. Adherence will be calculated and used in the analyses as a covariate.

5.5 COVID-19 Restrictions – Enacting March 2020

As of March 2020, UCLA has enacted several restrictions on our campus to prevent COVID-19 contraction and spread. In order to align with these standards, we are giving participants the option to participate virtually through web-based and telephone meetings. This will be offered for any appointment that is able to be completed remotely, as well as for both interventions the study is testing. This will include teleneuropsychological assessments as well. All remaining portions that are not possible to obtain remotely (e.g., MRI, venipuncture) will be obtained as close to the proposed visit date as possible.

We will also instill a COVID-19 Questionnaire to all active participants to ensure optimal safety reporting and to correlate with current psychiatric measures. This will be administered as a survey, with the responses coming verbatim from the participant. The survey will be completed at one time point, but we will continue to track participants' well-being through our administration of UKU.

6. STUDY PROCEDURES

All study assessments will be conducted in a private examination room at either at UCLA Semel Institute or the UCLA Motion Picture Television Fund Campus.

Screening Procedures (Screening / Visits 1a-c): The informed consent form will be reviewed with the participant during the first in-person visit. There will be general medical and psychiatric history taken, vital signs (blood pressure, pulse) (5 minutes duration), and an ECG (electrocardiogram) will be performed (25 minutes). The questionnaires and screening procedures are performed to determine eligibility. The initial visit will last approximately 2 hours.

Clinical Assessments will be performed in 2-3 visits due to participant's burden: (Tables 1;3). Diagnosis. The Structured Clinical Interview DSM-IVTR-5 (SCID)¹²¹ will be used to make a diagnosis of major depression or other mood disorders or rule out other diagnoses (e.g., psychosis and dementia) at screening. Inter-rater reliability for all instruments will be established at the beginning of the trial across both sites and all staff members on the first 5 recruited patients, it will be rechecked routinely twice a year for consistency throughout the study. Master level research associates supervised by the PI will be trained to reliability for the diagnostic interview (SCID) and other assessments. The current inter-rater correlation coefficient (ICC) for SCID ratings among SCID interviewers is ≥ 0.9 . A second level of reliability check is afforded by a bi-weekly diagnostic consensus conference during which diagnosis is also confirmed.

Blood Samples. During screening procedures between 1st in-person visit and visit 2, blood will be drawn by needlestick for routine laboratory testing and genetic analysis (15 minutes). The blood samples will be processed at the UCLA Clinical and Translational Research Center (CTRC). Approximately 8 tablespoons of blood will be drawn. This visit can be combined with either the visits for MRI or Cognitive testing visit.

Screening diagnostic / Neuropsychological Evaluation Visit (Visit 2):

[name] or a designated member from the study staff will conduct a neuropsychiatric evaluation using cognitive assessments during Visit 2 that takes about 2-3 hours.

Visit 3. Magnetic Resonance Imaging (MRI) Scan. One MRI brain scan will be performed. The scan will occur at the UCLA Brain Mapping Center. MRI Safety metal screening will be performed. Only 55 pts/arm will undergo the fMRI procedure.

Visit 4. Baseline visit will be performed within 2 months prior to initiation of the interventions with assessment of mood and vital signs (30 min)

Follow-Up Visits (Visits 4-9 and 12-13): Follow-up assessment will occur bi-weekly (every 2 weeks) for 12 weeks and then monthly in order to ensure safety. Each visit will last approximately 30 minutes. Interviews and questionnaires will be used to determine if the treatment is working and useful. Adherence will be monitored at each visit. At each follow-up visit, vital signs will be measured (5 minutes), practice and homework log will be reviewed, and questionnaires will be administered (25 minutes).

Weekly Tai Chi or Health and Wellness Education (12 classes): Weekly Tai Chi or health and wellness education training will occur every week for 60 minutes for 12 weeks. The weekly sessions will last approximately 60 minutes per class. Homework adherence and diaries will be monitored at each class.

Visits 10/11 and 14-19- Outcomes and Endpoints. 12 week follow-up visit (Visit 10/11): During the final visit, a physical, psychiatric examination, and a follow-up blood draw for genetic analysis will be repeated. MRI will be repeated at 12 weeks. The follow-up visit 12 will be split in 2 visits (for clinical, cognitive, laboratory, and MRI) will last 4 hours (1 hour MRI). The 6-month follow-up

visit (14/15) will be approximately 1.5 hours. Both the 12- or 24-month follow-up visit will be split in 2 visits (for clinical, cognitive, laboratory, and MRI) will last 4 hours (1 hour MRI). The Month 12/24 visit will be completed by only those participating in the MRI portion of the study. Since this visit was added onto the original study, some of the participants may have passed their Month 12/24 time point. We will allow this visit to occur any time succeeding the Month 12 mark, and will note the visit type by proximity of their timeline (ie: Participant completes visit at Month 17, would be assigned to Month 12 Visit).

